## 4.7 Discharge

Following the renal denervation procedure, the subject's blood pressure will be monitored every 4 hours post procedure until discharge, or for a maximum of 24 hours. At discharge a physical assessment will be performed and the subject's medication regimen will be reviewed and recorded. Discharge is expected to occur within 72 hours post procedure.

Adverse Events – check if any adverse events or adverse device effect occurred since enrollment of the patient into the Clinical Investigational study. Document the event in the hospital records and report the adverse event according to specifications in section 5.3.2.

## 4.8 Follow-up visits

Subjects will return for follow-up at 1 month ( $\pm 14$  days), 6 months ( $\pm 30$  days) post procedure and annual follow-up visits at 12, 24, 36, 48, and 60 months post-procedure ( $\pm 60$  days).

**The following will be evaluated / reviewed according to Table 1:**

### 4.8.1 Physical Assessment

The subject will have a physical assessment at every follow up visit to capture weight.

### 4.8.2 Medications

Medications will be recorded in addition to documenting changes to medications at each follow-up visit.

### 4.8.3 Office Blood Pressure

Office Blood Pressure measurements will be recorded as the average blood pressure of three measurements at each follow-up visit. Measurements should be taken according to Standard Joint National Committee VII Guidelines / ESC and ESH Guidelines  (Refer to Appendix A for Office Blood Pressure instructions).

### 4.8.4 24 hour Ambulatory Blood Pressure

24 hour Ambulatory Blood Pressure measurements should be taken according to Standard Joint National Committee VII Guidelines / ESC and ESH Guidelines  (Refer to Appendix B for 24 Hour Ambulatory Blood Pressure instructions) at each follow-up visit.

---

SJM CONFIDENTIAL AND PROPRIETARY

In addition to the daytime mean ABP, the night time mean, and 24 hour average ABP value will be collected. When using ABP ensure that at least two measurements per hour are taken during the person's usual waking hours (for example, between 08:00 and 22:00) and 1 measurement per hour are taken during the person's usual night time hours. The average value of at least 14 measurements taken during the person's usual waking hours should be used for calculation of mean daytime value.

#### **4.8.5 Blood and Urine Analysis**

Blood and urine samples will be collected and analyzed as listed below.

- Serum Creatinine – to be collected at 6M, 12M, 24M, and 60M follow-up visit.
- Estimated GFR (eGFR) – to be collected at 6M, 12M, 24M, and 60M follow-up visit.
- Hemoglobin A1c – to be collected at the 6M follow-up visit only
- Fasting glucose – to be collected at the 6M follow-up visit only
- Fasting insulin – to be collected at the 6M follow-up visit only
- Urine albumin to creatinine ratio – to be collected at the 6M, 24M, and 60M follow-up visit.

A true numeric value for the estimated GFR must be provided. If your local laboratory does not report the eGFR value beyond 60 mL/min/1.73 m^2 the center should use a sponsor-approved calculation tool to generate the value. The sponsor will provide an approved website(s) for this calculation to study centers.

#### **4.8.6 Echocardiogram (TTE)**

Transthoracic-echocardiogram (TTE) examinations will be conducted at approximately 6 sites at the 1M, 6M, 24M, and 60M follow-up visit. Each site is responsible for performing the 3D echocardiogram per each institutions standard of care echo protocol.

#### **4.8.7 NYHA Assessment**

NYHA Assessment will be evaluated at the 1M, 6M, 24M, and 60M follow-up visit and should be classified based on the definitions in Appendix C.

#### **4.8.8 EQ-5D 5L Quality of Life Questionnaire**

EQ-5D 5L questionnaire will be completed at 1M, 6M, 24M, and 60 M follow-up visit.

#### **4.8.9 Renal artery evaluation**

Renal artery evaluation will be completed at the 6M, 24M, and 60M follow-up visit. Duplex Ultrasound (U/S) is the recommended imagine modality, however this evaluation can be completed by either: computed axial tomography (CT scan), duplex ultrasonography, Doppler,

angiography, magnetic resonance (MR) angiography or non contrast magnetic resonance imaging.

If a renal artery evaluation is completed at any other time point this data will also be collected during the study.

#### **4.8.10 Adverse Events**

Confirm if any adverse events or adverse device effect occurred since the last visit and document in the hospital records. Report the adverse event according to specifications in section 5.3.2.

### **4.9 Clinical Investigation Termination**

Each subject will be followed for 5 years post renal denervation procedure or until time of death, loss of follow up, withdrawal or clinical investigation termination. The clinical investigation will be complete after all follow-up visits are performed, all data is received by the Sponsor and the database is locked. The study will be closed when a final report is written on the conclusions and analysis of the data.

Participation in this clinical investigation is voluntary. Subjects are free to withdraw from the clinical investigation at any time without reason. Should this occur, the reason for discontinuation must be recorded in the source documents. However, subjects should be strongly encouraged to complete the CIP required follow up. Should a subject wish to withdraw prior to completing 60 month follow-up, the investigator should request the subject to come in for a final visit and a Clinical investigation Termination CRF should be completed by the site and provided to the Sponsor.

At this visit the subject will undergo the following evaluations:

- Office Blood pressure measurement
- Blood/Urine labs

In a situation where a clinical investigation withdrawal is due to an adverse event the subject should be followed until resolution of that adverse event or determination that the subject's condition is stable.

Subjects must be informed about their right to withdraw from the investigation at any time and for any reason without sanction, penalty or loss of benefits to which the subject is otherwise entitled and withdrawal from the investigation will not jeopardize their future medical care or relationship with the investigator. Subjects will be asked to specify the reason for the termination, but have the right not to answer.

The investigator may decide to withdraw a subject from the investigation at any time. The subject's future care will not be influenced by a decision, voluntary or otherwise, to withdraw from the investigation. All reasonable efforts should be made to retain the subject in the clinical investigation until completion of the investigation.

Other reasons for termination or withdrawal include, but are not limited to, the following:

- Subject did not meet the inclusion/exclusion criteria

---

SJM CONFIDENTIAL AND PROPRIETARY

- Subject death (in case of subject death, cause must be documented)
- Subject and/or family request
- Subject non-compliance
- Subject lost to follow-up, defined as the following: a subject will be considered “lost to follow-up” after a minimum of 2 documented phone calls of a physician or delegate at the study site to the subject or emergency contact and a certified letter sent to the last known address
- Subject’s participation terminated by Investigator
- Study terminated by SJM
- The study terminated according to locally applicable regulations
- The study may be temporarily stopped or terminated, either at the local, national, or international level, at the request of Ethics Committees, regulatory authorities, or SJM.

#### **4.10 Description of post investigational provision of medical care**

When the subject’s participation in the clinical investigation has been completed (prematurely) or terminated, the subject will return to the medical care as per physician’s recommendation.

## **5 Clinical Investigation Conduct**

### **5.1 Ethics Committee**

A duly constituted EC representing the prospective study site must review and approve the subject informed consent and research authorization document, the study protocol, the prospective investigator’s participation in the study, and any other study related information to be provided to the subjects prior to subject enrollment. Additionally, the Investigator must be aware of and adhere to all EC requirements such as, but not limited to: the submission of progress reports, serious adverse events, and protocol deviations.

EC approval record should clearly identify:

- the date of the meeting
- constitution of the committee and voting members present at the meeting
- the approved version of the Clinical Investigation Plan
- the approved version of the Patient Information Sheet and subject Informed Consent
- the approved version of the Investigator’s Brochure
- the approved version of the Instructions for Use (IFU)

Approval from the EC is necessary prior to the start of the investigation. The original approval is to be filed in the Investigator Study Binder and a copy of the approval is provided to SJM prior to the first investigational assessment.

---

SJM CONFIDENTIAL AND PROPRIETARY

© 2012 – St. Jude Medical Cardiovascular Division: All rights reserved. No portion of this work may be reproduced in whole or in part without the express written permission of St. Jude Medical Cardiovascular Division.  
Clinical Investigational Plan: EnligHTN II

Any amendments to the protocol should be submitted to the relevant EC. The EC will be informed about SAEs and UADEs in accordance with local and national requirements.

Prior to SJM receiving data from the study site, the study protocol will be reviewed and approval obtained from the study site EC. There are no additional Board reviews for the study.

## **5.2 Ethical Basis**

This clinical investigation will be performed in accordance with the World Medical Association Declaration of Helsinki (Appendix F) and applicable local and national legal and regulatory requirements. Prior to starting the investigation, the Clinical Investigation Plan will be submitted together with associated documents including Patient Information Sheets, and subject Informed Consent Forms in the local language to the relevant EC for review.

## **5.3 Insurance**

St. Jude Medical, as the Sponsor, has taken out insurance for all subjects participating in this study in accordance with the requirements of the local laws.

## **5.4 Statements of Compliance**

The investigation will be performed in accordance with the most current versions of the World Medical Association (WMA) Declaration of Helsinki and any regional and/or national regulations, as appropriate.

The investigator shall not start enrolling subjects or requesting informed consent prior to obtaining Ethics Committee approval and authorization from the sponsor in writing for the investigation.

In case additional requirements are imposed by the Ethics Committee, they shall be followed, if appropriate.

As sponsor, SJM will maintain insurance for this investigation in accordance with the requirements of the applicable local laws.

## **5.5 Adherence to the Clinical Investigation Plan**

The Principal Investigator and delegates are required to adhere to the CIP in order to prevent subjects being exposed to unreasonable risks. The Principal Investigator and delegates are also required to be compliant with the signed Study Agreement, applicable national or local laws and regulations, and any conditions required by the appropriate EC or applicable regulatory authorities are expected as well. Instances of failure, intentionally or unintentionally, to adhere to the requirements of the CIP are considered a deviation and corrective action(s) may be taken to prevent these instances from occurring again.

In some cases failure to comply with the CIP may be considered failure to protect the rights, safety and well-being of subjects, since the non-compliance exposes subjects to unreasonable risks. For example, failure to adhere to the inclusion/exclusion criteria: these criteria are specifically defined by the Sponsor to exclude subjects for whom the device is not beneficial and the use involves unreasonable risks. This may be considered failure to protect the rights, safety

and well-being of the enrolled subject. Similarly, failure to perform safety assessments intended to detect adverse events may be considered failure to protect the rights, safety and well-being of the enrolled subject. Investigators should seek minimization of such risks by adhering to the CIP.

Simultaneously, in the event that adhering to the CIP might expose the subject to unreasonable risks, the investigator is also required to protect the rights, safety and well-being of the subject by intentionally deviating from the requirements of the CIP, so that subjects are not exposed to unreasonable risks. It is the responsibility of the investigator to provide adequate medical care to a subject enrolled in an investigation.

The PI shall promptly report any deviations from the CIP to the Sponsor that affects the rights, safety or well-being of the subject or the scientific integrity of the clinical investigation, including those which occur under emergency circumstances. The reporting of these deviations should be done as soon as possible but no later than 72 hours after the investigator becomes aware. The investigator shall also promptly notify the EC, as per their requirements.

Any corrective and preventive actions required by the EC must be complied with by the site.

The Sponsor will notify the EC as per their requirements.

### **5.5.1 Repeated non-compliance**

In the event of repeated non-compliance, as determined by the Sponsor, a Clinical Research Associate or sponsor representative will attempt to secure compliance by one or more of the following actions:

- Visiting the investigator
- Contacting the investigator by telephone
- Contacting the investigator in writing
- Retraining of the investigator

If an investigator is found to be repeatedly non-compliant with the signed agreement, the CIP or any other conditions of the clinical investigation, the Sponsor will either secure compliance or, at its sole discretion, terminate the investigator's participation in the clinical investigation.

## **5.6 Informed Consent Process**

### **5.6.1 General Process**

Provision of the Informed Consent is mandatory. Informed Consent is required from all patients prior to participation in the investigation. The process of obtaining Informed Consent shall comply with the most recent version of the Declaration of Helsinki, ISO 14155:2011 and all applicable regulations.

The Principal Investigator or his/her authorized designee will conduct the Informed Consent Process. This process will include a verbal discussion with the patient on all aspects of the clinical investigation that are relevant to the patient's decision to participate in the clinical investigation. It is crucial that this discussion is documented in the source documents (hospital records).

Prior to enrolling in the clinical study, patients shall be fully informed of the details of clinical study participation as required by applicable regulations and the study center's EC, and/or Head of Medical Institution. Informed consent must be obtained from each patient prior to any clinical study participation using the Patient Information Sheet (PIS) and Patient Informed Consent form (PIC) approved by both the Sponsor as well as that study center's EC, and/or Head of Medical Institution. Prior to the patient signing the PIS, the investigator or authorized delegate will fully explain to the patient the nature of the research, clinical study procedures, anticipated benefits, and potential risks of participation in the clinical study.

The patient will be provided with the EC approved patient information sheet and informed consent form that is written in a language that is understandable to them (native non technical language) and sufficient time is provided to the patient to consider participation and ask questions if necessary. The study site personnel will provide answers to the patient's questions.

If a patient is unable to read or write, the consenting shall be obtained through a supervised oral process. An independent witness shall be present throughout the process. The consent form must be signed and dated by the patient and by the person obtaining the consent attesting that the information was accurately explained and that informed consent was freely given.

The consent form must be signed and dated by the patient and by the person obtaining the consent.

If the patient does not sign and date the PIC, they cannot participate in the investigation. No further CIP required activities are allowed. If the patient has provided written informed consent, obtain signature and date from the Principal Investigator or authorized designee on the EC approved informed consent form.

In order to avoid any possible coercion or undue improper influence on, or inducement of the patient to participate, the Sponsor requests the investigator to only sign the informed consent form once the subject has signed and dated the document and therefore decided to participate in the investigation.

Informed Consent of a subject shall always be indicated by personally dated signature of the subject and by the investigator responsible for conducting the Informed Consent process.

The original signed consent document must be retained on file by the investigator and a copy of the signed consent document is provided to the subject (investigator's responsibility).

The subject's legal rights will not be waived, nor will it appear that these will be waived.

Important new information that becomes available throughout the clinical investigation will have to be provided in writing to new and existing subjects. If relevant, all affected subjects will be provided a new consent form to review and re-sign, should they decide to maintain participation in the investigation.

## 5.7 Adverse Event, Adverse Device Effect

### Definitions

The definitions provided below are in accordance to ISO 14155:2011 (E).

#### 5.7.1 Medical device

Any instrument, apparatus, implement, machine, appliance, implant, software, material or other similar or related article.

- Intended by the manufacturer to be used, alone or in combination, for human beings for one or more of the specific purpose(s) of
  - Diagnosis, prevention, monitoring, treatments or alleviation of disease,
  - Diagnosis, monitoring, treatment, alleviation of, or compensation for, an injury,
  - Investigation, replacement, modification, or support of the anatomy or of a physiological process,
  - Supporting or sustaining life,
  - Control of conception,
  - Disinfection of medical devices and
- Which does not achieve its primary intended action in or on the human body by pharmacological, immunological or metabolic means, but which may be assisted in its intended function by such means

#### 5.7.2 Adverse Event (AE)

Any untoward medical occurrence, unintended disease or injury, or untoward clinical signs (including abnormal laboratory findings) in subjects, users or other persons, whether or not related to the medical device.

Note: This definition includes events related to the medical device or the comparator.

Note: This definition includes events related to the procedures involved.

#### 5.7.3 Serious Adverse Event (SAE)

An adverse event that led to:

- Death
- A serious deterioration in the health of the subject, that either resulted in:
  - A life-threatening illness or injury OR
  - A permanent impairment to a body structure or a body function OR
  - An in-patient or prolonged hospitalization OR
  - A medical or surgical intervention to prevent life-threatening illness or injury or permanent impairment to a body structure or a body OR
  - A malignant tumor
- Fetal distress, fetal death or a congenital abnormality or birth defect

Note: A planned hospitalization for a pre-existing condition, or a procedure required by the CIP, without serious deterioration in health, is not considered a serious adverse event.

---

SJM CONFIDENTIAL AND PROPRIETARY

© 2012 – St. Jude Medical Cardiovascular Division: All rights reserved. No portion of this work may be reproduced in whole or in part without the express written permission of St. Jude Medical Cardiovascular Division.

Clinical Investigational Plan: EnligHTN II

#### **5.7.4 Adverse Device Effect (ADE)**

An adverse event related to the use of an investigational device.

Note: This definition includes adverse events resulting from insufficient or inadequate instructions for use, deployment, implantation, installation, or operation, or any malfunction of the medical device.

Note: This definition includes any event resulting from the use error or from intentional misuse of the medical device.

#### **5.7.5 Serious Adverse Device Effect (SADE)**

Adverse device effect that has resulted in any of the consequences characteristic of a serious adverse event.

#### **5.7.6 Unanticipated Serious Adverse Device Effect (USADE)**

A serious adverse device effect which by its nature, incidence, severity or outcome has not been identified in the current version of the risk analysis report.

#### **5.7.7 Anticipated Serious Adverse Device Effect (ASADE)**

A serious adverse device effect which by its nature, incidence, severity or outcome has been previously identified in the risk analysis report.

#### **5.7.8 Procedure for assessing, recording and reporting adverse events, adverse device effects, serious adverse events and serious adverse device effects:**

Safety surveillance and reporting will be done for all subjects enrolled in this investigation as described below.

Safety surveillance within this investigation and the safety reporting performed by the investigator, starts as soon as the subject is enrolled in this investigation (date of signature of the informed consent). The safety surveillance and the safety reporting will continue until the last investigational visit has been performed or the subject is deceased or the subject/investigator concludes his participation into the investigation.

For the purpose of this trial, all Serious Events (regardless of relatedness) and all Adverse Device Effects (regardless of severity) will be reported via an eCRF to the sponsor. All Serious Adverse Events and all Adverse Device Effects (serious or non-serious) are to be documented and reported by the investigator to the sponsor immediately but no later than 72 hours after becoming aware of the event.

Adverse events will be assessed by the investigator for relationship to the device and to the procedures involved.

---

SJM CONFIDENTIAL AND PROPRIETARY

© 2012 – St. Jude Medical Cardiovascular Division: All rights reserved. No portion of this work may be reproduced in whole or in part without the express written permission of St. Jude Medical Cardiovascular Division.  
Clinical Investigational Plan: EnligHTN II

- Procedure related: The AE is deemed related to the procedure if it occurred during the procedure but was not directly caused by the medical device.
- Device related: The AE is deemed device related if it was directly caused by the medical device.

Investigators are responsible for promptly reporting all SAEs and ADEs to the sponsor by completing the Adverse Event form. All unresolved AEs should be followed by the investigator until resolution is reached.

Note: Refer to Table 1 ‘Data Collection’ and Appendix G ‘Data Collection Method’.  
In case of EDC failure, notify Sponsor via Fax or via [[contact]](mailto:[contact]).

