### **3.12 Devices Used**

The EnligHTN™ Renal Denervation System is designed to deliver radiofrequency (RF) energy to the renal nerves to achieve targeted denervation. The system consists of the EnligHTN™ RF Ablation Generator (generator), the EnligHTN™ Renal Artery Ablation Catheter (ablation catheter), and the EnligHTN™ Guiding Catheter (optional).

The following market approved St. Jude Medical devices to be first used in this investigation are:

---

SJM CONFIDENTIAL AND PROPRIETARY

© 2012 – St. Jude Medical Cardiovascular Division: All rights reserved. No portion of this work may be reproduced in whole or in part without the express written permission of St. Jude Medical Cardiovascular Division.  
Clinical Investigational Plan: EnligHTN II

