#### 4.5 Renal Denervation Procedure

The renal nerve ablation should be performed according to the EnligHTN™ Renal Denervation System Instructions for Use (IFU).

The renal denervation procedure should always be done with the aid of fluoroscopy. With the patient under local anesthesia, an introducer sheath will be inserted into the femoral artery using the standard percutaneous technique (modified Seldinger technique). A heparin bolus of 3000 to 5000 units will then be administered intravenously or per institution's standard of care. An 8 French guiding catheter sheath will be inserted to engage each main renal artery sequentially with the angiograms recorded. Images of the left and right main renal arteries will be recorded using the non-ionic contrast and the diameter and length of each of the main renal arteries will be measured.

Prepare the patient for standard electrosurgery. Select an appropriate basket size of the Basket Renal Denervation Catheter (small size for patient with renal artery diameter between 4mm and 6mm and large size for patient with renal artery diameter between 5.5mm and 8mm) should be chosen. The Basket Renal Denervation Catheter will be inserted with the tip of the catheter positioned proximal to the bifurcation of one of the main renal arteries and the corresponding images will be recorded. The basket on the Renal Denervation Catheter will then be opened, while the impedance of each electrode on the basket will be monitored. To begin the ablation, the "START" button on the RF Generator will be pressed with the impedance, temperature and RF energy delivery monitored and recorded during the process. The investigator will decide the location(s) and number of ablation sites/lesions (4 to 8 ablation sites/lesions are recommended) in the main renal artery. When the ablation procedure is completed in this main renal artery, the basket on the Catheter will be withdrawn from the artery with the Basket Renal Denervation Catheter fully closed. Images of the renal artery using the non-ionic contrast will be recorded. Any signs of renal artery irregularities (vasospasm, stenosis or dissection) will be checked.

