## **6 Risks and Benefits of the Clinical Investigation**

### **6.1 Anticipated Adverse Events and Adverse Device Effects**

Possible adverse events associated with the renal denervation procedure include, but are not limited to:

- Acute renal injury (renal infarction, renal hematoma)
- Renal vascular injury (renal artery dissection, renal artery thrombosis, renal artery stenosis)
- Collateral tissue injury
- Malignant or accelerated hypertension
- Symptomatic hypotension
- Access site complications (arteriovenous fistula, access site thrombosis, embolisation, pseudo-aneurysm, hematoma, limb ischemia, femoral nerve injury, or seroma)
- Disseminated intravascular coagulation
- Infection (access site infection or systemic infection)
- Renal failure
- Decompensated heart failure
- Myocardial infarction
- Neurologic event (acute ischemic or hemorrhagic brain injury)
- Respiratory compromise
- Pain, including Back Pain
- Death
- Drug reactions
- Contrast allergies etc
- Bradycardia
- Vasospasms
- Vasovagal episodes

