### **7.4.2 The Secondary objectives**

#### **7.4.2.1 Safety Acute data (30 days post procedure)**

- The peri-procedural events within 30 days post procedure will be summarized as percentage of patients defined as:

$$\frac{\text{Number of subjects with peri procedural events within 30 days post procedure}}{\text{Number of subjects at baseline for that population}} * 100$$

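### Section 5.7.8 can label late procedural complications as related to neither procedure nor device, and the plan's adverse-event reporting rules conflict over what reaches the 30-day safety count

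*Combined protocol and SAP*

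**What the plan says.** **Endpoint.** Section 3.2 gives one acute safety objective, peri-procedural events to 30 days. Section 7.4.2.1 states: "The peri-procedural events within 30 days post procedure will be summarized as percentage of patients". The numerator is subjects with such an event; the denominator is subjects at baseline in the population concerned. Nothing says which event types, what seriousness or what relatedness qualifies. Section 7.2 names these events among the considerations behind about 500 patients, with no formal power analysis. Section 7.4 calls for results overall and by Groups A, B and C.

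**Relatedness.** Section 5.7.8: "The AE is deemed related to the procedure if it occurred during the procedure but was not directly caused by the medical device". An event is device related there only if the device directly caused it. Section 5.7.4 defines an ADE more widely, as "An adverse event related to the use of an investigational device", and includes use error and inadequate instructions.

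**Reporting.** Section 5.7.8 says that "all Serious Events (regardless of relatedness) and all Adverse Device Effects (regardless of severity) will be reported via an eCRF to the sponsor", and repeats the same two classes for the Adverse Event form. Section 12.3.2 has the Clinical Event Committee (CEC) adjudicate those two classes. The general adverse event definition in 5.7.2 is wider: "Note: This definition includes events related to the procedures involved".

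**Other reporting text.** Section 4.1 says adverse events need reporting from consent onward and points to Section 5.3. Sections 4.7 and 4.8.10 ask sites to check for any adverse event or ADE, document it in the hospital record and report it under 5.3.2. Section 12.1 has the sponsor ensure that all adverse events and ADEs are reported. Section 5.3 is Insurance, and there is no 5.3.2.

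**The concern.** Relatedness in 5.7.8 turns on timing for the procedure and on direct causation for the device, while the acute endpoint runs to day 30. Section 6.1 anticipates complications that can appear after the subject leaves the laboratory, such as access site infection. Under 5.7.8 these can carry the same relatedness label as a coincidental illness, so any safety table broken down by investigator-assessed relatedness would misattribute them.

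The reporting conflict matters for a different reason. The procedure uses items outside the listed system: according to 4.5, "an introducer sheath will be inserted into the femoral artery using the standard percutaneous technique", and contrast is given. Section 3.12 lists only the generator, the ablation catheter and the optional guiding catheter. Section 6.1 anticipates access site hematoma and contrast allergy. Such an event, if non-serious and not judged an ADE, is an adverse event under 5.7.2 but carries no duty under 5.7.8 to reach the sponsor or the CEC. A site following 4.1 or 4.7 might report it, while a site following 5.7.8 need not. This percentage is the only stated acute safety objective, so readers need to know which events it covers.

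**Working it through.** There is no plan figure to reproduce: the documents give no expected event rate or precision target. The check is a comparison of the rules, followed by the weight of one subject.

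**Step 1. Apply the rules to four hypothetical cases.**

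| Case | Label under 5.7.8 | AE form required by 5.7.8 | Causally related to procedure or device |
|---|---|---|---|
| (i) Serious access site infection, day 5, not directly caused by the device | neither | yes (serious) | yes |
| (ii) Non-serious access site hematoma, day 1, from the introducer sheath, not judged an ADE | neither | no | yes |
| (iii) Unrelated serious event, day 20 | neither | yes (serious) | no |
| (iv) Non-serious ADE during the procedure, directly caused by the device | device related | yes (ADE) | yes |

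The label does not separate (i) from (iii), although one is a procedural complication and the other is not. An event related to use of the device but not directly caused by it would be an ADE under 5.7.4 and yet not device related under 5.7.8.

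**Step 2. Does the label change the 30-day count?** Section 7.4.2.1 has no relatedness condition, so (i) is counted whatever its label. The same absence lets (iii) in.

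**Step 3. Does the reporting rule change the count?**
- Serious events plus ADEs, no relatedness filter: (i), (iii), (iv) = 3.
- Any event causally related to procedure or device, serious or not: (i), (ii), (iv) = 3, of which 5.7.8 requires reporting of (i) and (iv) only = 2.

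Let a be the number of subjects whose only qualifying event is non-serious and not an ADE, and b the number counted only for an unrelated serious event. If the second reading is intended but 5.7.8 governs reporting, then

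reported minus intended = (b − a)/n × 100.

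Here a = 1 and b = 1, so the net is (1 − 1)/n × 100 = 0, although two subjects are classified differently. The documents give neither a nor b. If only serious events and ADEs are intended, nothing is missed.

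**Step 4. Weight of one subject (100/n).**
- All subjects, n = 500 (7.3): 100/500 = 0.2 percentage points.
- Group A at its minimum of 100 (4.4.1): 100/100 = 1.0 point.
- Group B or C at its minimum of 50 (4.4.2, 4.4.3): 100/50 = 2.0 points.

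The minimums sum to 100 + 50 + 50 = 200 of about 500, so the groups cannot all be at their minimum.

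**Step 5. Where do the broken references lead?** Sections 3.6 and 4.1 cite 5.2 for the consent process, which is now 5.6, a shift of four sections. The same shift takes 5.3 to 5.7, so the references are probably stale. Taken literally, however, it takes 5.3.2 to 5.7.2, the general adverse event definition, and not to 5.7.8. The references therefore cannot be assumed to carry the narrower limit.

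**The case against.** The strongest case against the point has four parts.

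- **Four sections speak of reporting adverse events generally.** This stands. A reader might infer from 5.7.8 alone that non-serious procedural events are simply not collected; the documents do not support that. What they show is a conflict. Section 5.7.8 is the only place that sets out a reporting procedure, and three of the four wider passages defer to a section that does not contain one.
- **The ADE definition is broad.** Femoral access exists to deliver the catheter, so an investigator could fairly report an access site hematoma as an ADE. This stands, and the remaining gap may be small. It does leave the count to each investigator's reading across about 40 sites.
- **The label removes nobody from the endpoint.** This stands. A reader might infer that late complications drop out of the rate. That would need a relatedness filter, which 7.4.2.1 does not state. Serious events are reported whatever their relatedness, and the CEC determines relationship for the events it reviews. The wording in 5.7.8 still governs the investigator's assessment.
- **Documents not shown may settle part of this.** The CEC charter is separate, and Appendix H places the form data points under separate cover; the procedure and discharge forms could capture acute events. Events not entered on the adverse event form would also remain in hospital records and subject files (4.7, 4.8.10, 8.3), and 12.1 lets the sponsor ask for more documentation. The definition of the endpoint nonetheless belongs in 7.4.2.1.

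**Conclusion.** Two faults hold and should be fixed. First, the relatedness rules in 5.7.8 can misattribute procedural complications that appear after the procedure but inside the 30-day window, and they disagree with 5.7.4 on what device related means. This affects attribution, not the 30-day count as written. Second, the plan conflicts with itself on which adverse events must be reported, so a non-serious procedural event not judged an ADE may not reach the count.

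A reader might go further and conclude that the 30-day rate is biased low. The documents do not support this, because unrelated serious events can enter the same numerator and neither a nor b is given. The size and net direction cannot be derived. The effect on the rate is nil if only serious events and ADEs are intended, which is a natural reading of 5.7.8 but is not stated in 7.4.2.1. The study is descriptive with no hypothesis test, so no formal decision depends on the rate; what suffers is its meaning and its comparability across sites and groups.

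**What to change.** 1. **Section 5.7.8, relatedness.** Define *procedure related* by causal relation to any procedural step, whatever the onset date, and align *device related* with the ADE definition in 5.7.4.
2. **Reporting scope.** Reconcile 4.1, 4.7, 4.8.10, 5.7.8 and 12.1, and correct the references to 5.3 and 5.3.2. Then choose one of two routes:
   - require Adverse Event form entry for all procedure- or device-related events, serious or not, from procedure start to day 30; report subjects with serious and with non-serious events separately in 7.4.2.1; and say in 12.3.2 whether the CEC or the investigator assesses the non-serious ones; or
   - if only serious events and ADEs are intended, say so in 7.4.2.1, state whether unrelated serious events count, and label the rate accordingly.

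**Cost.** A short amendment either way. The first route adds some adverse event forms over 30 days per subject and may raise the stated event rate; sites already document these events in the hospital record. The second route needs wording changes only, with no extra data collection.
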